##### **11.4.4.2 Pharmacodynamic/Activity Data**

The evaluation of PD biomarkers will be based on absolute and percent change from baseline in serum levels of total IgG, IgG subtypes (IgG1-4), immunoglobulin A (IgA), immunoglobulin M (IgM), albumin, and CIC that will be summarized by cohort and timepoint.

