Study drug, dosage, and administration	
Study drug: SYNT001
 
Dosage:
 
Cohort 1: 10 mg/kg, 5 weekly IV doses
 
Cohort 2: ≤30 mg/kg, 5 weekly IV doses
 
Cohort 3: ≤30 mg/kg, 14 weekly IV doses
 
Cohort 4 (optional cohort): ≤45 mg/kg, ≤14 weekly IV doses
 
Product presentation and preparation:
 
SYNT001 provided as a liquid at a nominal concentration of 50 mg/mL. SYNT001 is diluted in dextrose 5% in water (D5W) to prepare the solution for infusion.
 
Route of administration: IV in 250 mL over 1 hour ± 15 minutes

Control, dose, and route of administration	Not applicable																										
Duration of subject participation	
The duration of subject participation for each cohort is as follows:
 
  
 Cohorta	Screening	Treatment	Follow-up	Maximum Total	
 
 Days	Weeks	
   
 1	≤14 days	28 days	84 days	126 days	18 weeks	
 
 2	≤14 days	28 days	84 days	126 days	18 weeks	
 
 3	≤14 days	91 days	84 days	189 days	27 weeks	
  
 
a. Planned dose and duration of subject participation for Cohort 4 (optional cohort) will be determined following DEC data review. All available data will be considered.
	Cohort a	Screening	Treatment	Follow-up	Maximum Total		Days	Weeks	1	≤14 days	28 days	84 days	126 days	18 weeks	2	≤14 days	28 days	84 days	126 days	18 weeks	3	≤14 days	91 days	84 days	189 days	27 weeks
Cohort a	Screening					Treatment	Follow-up	Maximum Total																			
		Days	Weeks																								
1	≤14 days	28 days	84 days	126 days	18 weeks																						
2	≤14 days	28 days	84 days	126 days	18 weeks																						
3	≤14 days	91 days	84 days	189 days	27 weeks																						

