## 2. BACKGROUND AND RATIONALE

SYNT001, a humanized, affinity-matured IgG4-kappa monoclonal antibody (mAb), blocks immunoglobulin G (IgG) and circulating IgG immune complex (CIC) interactions with the neonatal crystallizable fragment receptor (FcRn), and inhibits the varied roles played by FcRn in the immune response.

Through specific and high affinity blockade of FcRn, SYNT001 has been shown to increase the catabolism of IgG and CIC in healthy volunteers and is predicted to block the ability of CIC to activate intracellular signaling events associated with binding to FcRn. This predicts that SYNT001 will also accelerate degradation of endogenous circulating IgG autoantibodies and IgG-IC specifically involved in the pathogenesis of autoimmunity. Blocking FcRn interactions with CICs further predicts that SYNT001 will have consequences for innate and adaptive cellular immunity. In the first instance, blocking multimeric CIC interactions with FcRn within antigen-presenting cells should result in inhibition of CIC inflammatory cytokine production and release by these cells. In addition, as FcRn determines the intracellular itinerary of CICs within and among compartments important in cellular immunity, it is further anticipated that SYNT001 will block antigen processing and presentation of antigens contained within CIC that otherwise lead to CD8+ and CD4+ T cell activation. Thus, SYNT001 is expected to specifically target immune functions associated with IgG and CIC that are involved in certain IgG-mediated autoimmune conditions.

SYNT001 targets key mechanisms contributing to pathology in a variety of IgG-mediated autoimmune disorders, including warm autoimmune hemolytic anemia (WAIHA) pemphigus, pemphigoid, myasthenia gravis, immune thrombocytopenic purpura (ITP), and chronic inflammatory demyelinating polyneuropathy (CIDP).

While current treatments for certain autoimmune disorders, including chronic steroids, immunosuppressants, intravenous immunoglobulin (IVIG), plasmapheresis, and anti-CD20 mAbs, such as rituximab, can be effective, they are associated with significant adverse effects, and delayed or non-durable responses.

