### 3.6 Exploratory Endpoints

The exploratory endpoints of this study are as follows:

- The exploration of SYNT001 mechanisms of action and effects of SYNT001 on pathophysiology summarized by cohort and timepoint as determined by:
  - Complement component 3 (C3) levels by nephelometry
  - Anti-epithelial cell antibody (AECA) titers by indirect immunofluorescence
  - Fc gamma R2A receptor (*FCGR2A*) single-nucleotide polymorphisms (SNP) by genotyping
  - Presence of disease and inflammatory markers by RNAseq (RNA sequencing)
  - Immunophenotyping via measures of T cells, monocytes, NK cells and B cells by flow cytometry
  - Urine IgG levels to explore SYNT001 distribution and elimination

- Exploratory biomarkers to investigate immune response associated with pemphigus
- The evaluation of corticosteroid use during the study will be summarized by cohort and timepoint
- The assessment of SYNT001 impact on subject's HR-QoL by responses to the Autoimmune Bullous Disease Quality of Life (ABQoL) questionnaire and Skindex-29 scores summarized by cohort and timepoint
- The qualitative assessment of changes in appearance of skin and mucosal lesions as determined by photography presented by cohort and timepoint
- The determination of SYNT001 levels in skin biopsies across timepoints (skin biopsies optional)

Further details on the statistical and analytical plans for these endpoints are available in [Section 11](#).

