#### **11.4.3.2 Dose Selection Data**

The evaluation of SYNT001 based on total IgG levels and responses on the PDAI total activity score from baseline will be summarized using descriptive statistics. Descriptive statistics will include mean, SD, coefficient of variation (CV), median, minimum, and maximum. The determination of dose and dosing duration of SYNT001 that achieves (i) total IgG level nadir decrease by  $\geq 60\%$  and  $\leq 90\%$  from baseline and (ii) a PDAI total activity score of  $\geq 50\%$  reduction from baseline to allow further clinical development in subject with pemphigus (*vulgaris* or *foliaceus*).

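### SYNT001 is an IgG4 antibody, and the plan does not separate it from the subject's own IgG; if the assays detect it, the IgG4 and total-IgG falls are understated

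*Protocol*

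**What the plan says.** The Background (section 2) describes the drug as "SYNT001, a humanized, affinity-matured IgG4-kappa monoclonal antibody (mAb"). The Synopsis dosing entries include "Cohort 1: 10 mg/kg, 5 weekly IV doses" and "Cohort 2: ≤30 mg/kg, 5 weekly IV doses", with up to 45 mg/kg in the optional Cohort 4.

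Measured IgG enters the analysis in two places:

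- **Secondary pharmacodynamics, section 11.4.4.2.** "The evaluation of PD biomarkers will be based on absolute and percent change from baseline in serum levels of total IgG, IgG subtypes (IgG1-4"), with IgA, IgM, albumin and immune complexes, summarised by cohort and timepoint.
- **Primary dose selection, section 11.4.3.2.** "The evaluation of SYNT001 based on total IgG levels and responses on the PDAI total activity score" is to be summarised descriptively. The target is then fixed: "The determination of dose and dosing duration of SYNT001 that achieves (i) total IgG level nadir decrease by" at least 60% and at most 90%, together with a PDAI reduction of at least 50%.

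Table 8 schedules total IgG and all four subclasses at the same visits. On dosing days the draw is pre-dose (footnotes to Tables 2 to 4). Cohort 1 is also sampled 24 and 48 hours after the first and fifth infusions (Days 1, 2, 29 and 30). The protocol names no assay for serum IgG or its subclasses and gives no half-life for SYNT001.

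**The concern.** The baseline sample contains no drug and on-treatment samples do. An assay that recognises human IgG, or human IgG4, would report endogenous IgG plus SYNT001, and the percent change would be computed on that sum. The error has one direction: the fall looks smaller than it is.

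Two results are at stake. The secondary IgG4 summary could show a rise while the subject's own IgG4 is falling. The primary criterion compares total IgG with a fixed 60% cut. At a given baseline and half-life the understatement is proportional to dose, so a dose near the cut could miss it because of its own residual drug.

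The timing matters too. The Dose Escalation Committee uses total IgG when recommending doses (Table 5 footnote, section 9.5.1), whereas the SAP need only be final before database lock (section 11.4.1). A correction made only in the SAP could come after those decisions.

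**Working it through.** **The protocol's own figures.** Section 10.3.3 gives expected IgG after 50% and 80% falls. 1150 × 0.5 = 575; 600 × 0.5 = 300; 1150 × 0.2 = 230; 600 × 0.2 = 120 mg/dL. All four reproduce.

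**Inputs from the protocol.** Doses of 10, 30 and 45 mg/kg, weekly; mean baseline IgG 1150 mg/dL (section 10.3.3); lowest eligible baseline 600 mg/dL (section 6.3).

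**Assumptions not in the protocol.** The assay reads the drug fully; one compartment; distribution volume V = 0.05 L/kg (range 0.04 to 0.06); half-life h of 1 to 7 days; baseline IgG4 of 40 or 50 mg/dL.

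**Formulas.** Single-dose peak C0 (mg/dL) = dose / V / 10. Drug at t days after the fifth weekly dose = C0 × Σ 2^(−(t+7i)/h), i = 0 to 4. Understatement in percentage points = 100 × drug / baseline.

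**Peak.** At V = 0.05, C0 is 20, 60 and 90 mg/dL at 10, 30 and 45 mg/kg. At V = 0.04 it is 25, 75 and 112.5.

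**Total IgG, trough 7 days after dose 5** (V = 0.05). Cells show drug in mg/dL, then points lost at baseline 1150 / 600.

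| Half-life | 10 mg/kg | 30 mg/kg | 45 mg/kg |
|---|---|---|---|
| 1 day | 0.2; 0.0 / 0.0 | 0.5; 0.0 / 0.1 | 0.7; 0.1 / 0.1 |
| 3 days | 4.9; 0.4 / 0.8 | 14.8; 1.3 / 2.5 | 22.3; 1.9 / 3.7 |
| 5 days | 12.1; 1.1 / 2.0 | 36.3; 3.2 / 6.1 | 54.5; 4.7 / 9.1 |
| 7 days | 19.4; 1.7 / 3.2 | 58.1; 5.1 / 9.7 | 87.2; 7.6 / 14.5 |

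**Crossing the cut.** A true 65% fall reads below 60% once drug exceeds 0.05 × baseline: 30 mg/dL at 600, 57.5 mg/dL at 1150. At 30 mg/kg this happens from the 5-day row at baseline 600 (36.3 > 30) and only just in the 7-day row at baseline 1150 (58.1 > 57.5).

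**Sensitivity at V = 0.04.** Take a true 63% fall and the weekly steady-state trough C0·r/(1−r), r = 2^(−7/h). With h = 3 and 30 mg/kg, r = 0.198 and drug = 75 × 0.198 / 0.802 ≈ 18.6 mg/dL. The reading is 59.9% at baseline 600 and 61.4% at 1150. At 45 mg/kg it is 58.4% and 60.6%. With h = 5 the readings are 55.4% and 59.0% at 30 mg/kg, and 51.6% and 57.0% at 45 mg/kg. With h = 1 the reading is 62.9% in every case.

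**IgG4, Cohort 1, Day 1.** V = 0.04, baseline 50, true fall 5%. With h = 1: drug = 25 × 0.5 = 12.5, and (47.5 + 12.5)/50 − 1 = +20%. With h = 5: drug = 21.8, reading +39%. At V = 0.06 and h = 1: drug = 8.3, reading +12%. The sign is wrong whenever drug / baseline exceeds the true fractional fall.

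**IgG4, Cohort 1, Day 29.** V = 0.05, baseline 40, true fall 70%, so endogenous IgG4 is 12. Drug is 10.1, 19.8 and 35.1 mg/dL for h = 1, 3 and 7. The readings are (12 + 10.1)/40 − 1 = −45%, then −20% and +18%. The fall is badly understated throughout, and the sign flips only at the long half-life.

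**IgG4 at trough after dose 5.** Same baseline and true fall. At 10, 30 and 45 mg/kg it reads −58%, −33% and −14% for h = 3, and −22%, +75% and +148% for h = 7. For h = 1 it stays between −68% and −70%.

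**The case against.** The premise is conditional. No IgG assay is named (nephelometry is specified only for C3), and laboratory detail is left to a manual that is not shown. A reader might infer that the assays do count SYNT001, perhaps because section 3.6 lists "Urine IgG levels to explore SYNT001 distribution and elimination". The documents do not support that. A urine endpoint worded this way does not establish what the serum assays react with.

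A reader might also infer that the dose-selection criterion is biased as planned, or that the 60% cut alone settles the minimum effective dose. Neither follows. Dosing-day samples are pre-dose, when drug is lowest. The 24- and 48-hour draws exist only in Cohort 1 at 10 mg/kg (Table 6), and a minimum over visits tends to pass over readings raised by drug. The PDAI condition must also be met, and the committee weighs safety and clinical outcomes as well. At the 1150 mg/dL mean with a 3-day half-life, a true 63% fall still passes at 30 and 45 mg/kg, even at the smaller volume.

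Subtracting the drug level wherever a PK sample exists may look like the obvious remedy. For the nadir it would do harm. Cohort 2 has one on-treatment pre-dose PK sample (Day 28) and Cohort 3 has one (Day 91). Correcting that visit alone would pull the nadir toward it.

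All of this limits the size and the remedy. The gap remains: no serum IgG analysis separates drug from endogenous IgG, and if the assay reacts the error runs one way.

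**Conclusion.** The point holds in conditional form. SYNT001 is an IgG4, and sections 11.4.3.2 and 11.4.4.2 analyse measured total IgG and IgG4 without distinguishing it from endogenous IgG. If the assays detect it, the fall is understated.

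IgG4 is the firmer part because its baseline is small. Cohort 1 Day 1 reads as a rise at every half-life and volume tried, given a 50 mg/dL baseline and a true 5% fall. Later on-treatment values are understated or reversed, depending on half-life.

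For total IgG at trough, the bias is negligible at a half-life near 1 day. At 5 to 7 days and 30 mg/kg it is 3.2 to 9.7 points, largest near a 600 mg/dL baseline, and it can then move a result across the 60% cut. Which case applies cannot be settled from the protocol, because assay reactivity, half-life, volume and baseline IgG4 are all unstated.

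The documents support saying that a higher dose may look less effective than it truly is. They do not support saying that it will look less effective than a lower dose. The change is worth making because it is cheap and protects both a reported secondary endpoint and the dose-selection criterion.

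**What to change.** - **Section 11.4.3.2.** Add a supportive analysis that repeats the 60-90% nadir criterion on IgG1+IgG2+IgG3. These subclasses are already collected at every IgG visit and do not include the drug. Keep total IgG as the stated criterion.
- **Section 11.4.4.2.** State whether the total-IgG and IgG4 assays detect SYNT001. If they do, state that uncorrected on-treatment IgG4 will not be interpreted as a pharmacodynamic effect.
- **Drug-subtracted values.** Limit drug-subtracted IgG and IgG4 to a descriptive display at the Cohort 1 visits with matched PK samples (Days 1, 2, 5, 28, 29, 30 and 33). Do not mix corrected and uncorrected visits in any nadir.

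The cost is wording, one derived variable and an enquiry to the laboratory, with no added samples or assays. There is a small downside: the three-subclass sum leaves out endogenous IgG4 and carries the measurement error of three assays, so it supports the total-IgG criterion and does not replace it.

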##### **11.4.4.3 Immunogenicity Data**

Immunogenicity results will be summarized by cohort and timepoint. Descriptive statistics will include mean, SD, CV, median, minimum, and maximum.

#### **11.4.4.4 PDAI Data**

PDAI results will be summarized by score (total activity score, total damage score), cohort, and timepoint. Descriptive statistics will include absolute change from baseline, and percent change from baseline. PDAI will also be summarized by disease severity category, mild (0 to 8), moderate (9 to 24), and severe ( $\geq 25$ ).

#### **11.4.5 Analysis of Exploratory Endpoints**

##### **11.4.5.1 Corticosteroid Use**

The evaluation of corticosteroid use during the study will be summarized by cohort and timepoint.

##### **11.4.5.2 Health-Related Quality of Life Data**

HR-QoL results from the ABQoL and Skindex-29 assessments will be summarized by cohort and timepoint

##### **11.4.5.3 Photography**

The qualitative assessment of changes in appearance of skin and mucosal lesions as determined by photography presented by cohort and timepoint.

#### **11.5 Interim Analysis**

No interim analysis is planned.

## **12. STUDY MANAGEMENT**

### **12.1 Regulatory and Ethical Considerations**

#### **12.1.1 Ethical Conduct**

The study must fully adhere to the principles outlined in “Guideline for Good Clinical Practice” ICH E6 Tripartite Guideline (January 1997), and in general, be conducted in a manner consistent with the principles described in the Declaration of Helsinki. The Investigator will ensure that the conduct of the study complies with the basic principles of GCP as outlined in the current version of 21 CFR, subpart D, Part 312, “Responsibilities of Sponsors and Investigators”, Part 50, “Protection of Human Subjects”, and Part 56, “Institutional Review Boards”.

#### **12.1.2 Informed Consent**

A signed informed consent form (ICF) in compliance with 21 CFR, Part 50.25(a) and Part 50.25(b) and the ICH guidelines, will be obtained from each subject before the subject is entered into the study and before any study screening procedure is performed that involves risk. The method of obtaining and documenting the informed consent will comply with ICH GCP and all applicable laws and regulations and will be subject to approval by the Sponsor.

The Investigator, or designee, is responsible for obtaining written informed consent from each subject (or the subject’s legally authorized representative) participating in this study after a thorough and clear explanation of the objectives, procedures, anticipated benefits, and potential hazards of the study. In the case where the subject is unable to read, an impartial witness should be present during the entire informed consent discussion. After the subject has orally consented to participation in the trial, the witness’ signature on the form will attest that the information in the consent form was accurately explained and understood. The study site must retain the original ICF and a copy must be provided to the subject or to the subject’s legally authorized representative. If applicable, it will be provided in a certified translation of the local language.

The Sponsor, or designee, must review the signed ICF against any proposed deviations from a sample ICF the Sponsor has supplied to each site. The final IRB-approved document must be provided to the Sponsor for regulatory purposes.

The eCRF for this study contains a section for documenting informed subject consent, and this must be completed appropriately. Signed ICFs must remain in each subject’s study file and must be available for verification by site monitors at any time. If new safety information results in significant changes in the risk/benefit assessment, the consent form should be reviewed and updated as necessary. All subjects (including those already being treated) should be informed of the new information, should be given a copy of the revised form, and should give their consent to continue in the study.

#### **12.1.3 Subject Confidentiality and Privacy**

As applicable, in accordance with the Health Insurance Portability and Accountability Act (HIPAA), and associated privacy regulations, a patient authorization to use personally

identifiable health information may be required from each patient before research activities begin.

The Investigator must ensure that subjects' anonymity will be maintained and that their identities are protected from unauthorized parties. On eCRFs or other documents submitted to the Sponsor, subjects should be identified by an identification code and not by their names. The Investigator should keep a subject enrollment log showing codes, names, and addresses. The Investigator should maintain documents intended for storing onsite (eg, subjects' written consent forms) in strict confidence.

All study drugs, subject bodily fluids and tissue, and/or other materials collected shall be used solely in accordance with this protocol, unless otherwise agreed to in writing by the Sponsor.

#### **12.1.4 Future Use of Stored Specimens**

Not all the tissue and blood components obtained during this study may be required for the tests that are part of the clinical trial. Available samples may be used for additional research. This research will help to understand disease subtypes, drug response, and AEs, and possibly identify new drug targets or biomarkers that predict subject response to treatment. The use of the samples for internal research will adhere to the guidelines defined by the FDA in "Guidance on Informed Consent for In Vitro Diagnostic Device Studies Using Leftover Human Specimens that are Not Individual Identifiable" (issued 25 April 2006) and the European Medicines Agency (EMA) "Reflection Paper on Pharmacogenetic Samples, Testing and Data Handling" (Doc. Ref. EMEA/CHMP/PGxWP/201914/2006; 15 November 2007). If a subject requests destruction of their tissue and blood samples and the samples have not yet been de-identified, the Sponsor will destroy the samples as described in the FDA guidance. The Sponsor will notify the Investigator in writing that the samples have been destroyed.

#### **12.2 Study Administration**

The study administration structure is provided in [Table 10](#).

### 12.2.1 Institutional Review Board Approval

This study is being conducted under US IND 132727. This protocol (and any modifications) and appropriate consent procedures must be reviewed and approved by the site-specific IRB before the study is initiated. The IRB must operate in accordance with the current federal or local regulations. The Investigator will send a letter or certificate of IRB approval to the Sponsor (or designee) before subject enrollment and whenever subsequent modifications to the protocol are made.

### 12.2.2 Data Handling and Record Keeping

All data will be entered in a validated electronic data capture system using single data entry. Standard procedures (including following data review guidelines, manual clinical review based on subject profiles, computerized validation to produce queries, and maintenance of an audit file, which includes all database modifications) will be followed to ensure accurate data. Clinical personnel will review all data listings for outliers, data inconsistencies, and spelling errors.

### 12.2.3 Data Protection

The Investigator agrees that all information received from the Sponsor, including but not limited to the IB, this protocol, eCRFs, the INDs, and any other study information remain the sole and exclusive property of the Sponsor during the conduct of the study and thereafter. This information is not to be disclosed to any third party (except employees or agents directly involved in the conduct of the study or as required by law) or otherwise into the public domain without prior written consent from the Sponsor.

### 12.2.4 Study Site Regulatory Documentation

The Investigator must maintain adequate and accurate records to enable the conduct of the study to be fully documented and the study data to be subsequently verified. These documents should

be classified into 2 separate categories as follows: (1) Investigator's study file and (2) subject clinical source documents (see Section 12.2.5).

The Investigator's study file will contain the protocol and protocol amendments, eCRFs, query forms, IRB and governmental approval with correspondence, sample informed consent, drug records, staff curriculum vitae and authorization forms, and other appropriate documents and correspondence.

Subject clinical source documents (usually predefined by the project to record key efficacy and safety parameters independent of the eCRFs) may include subject hospital/clinic records, physician's and nurse's notes, appointment book, original laboratory reports, ECG, electroencephalogram, X-ray, pathology and special assessment reports, signed ICFs, consultant letters, and subject screening and enrollment logs. The Investigator must keep these two categories of documents on file for at least 2 years following the marketing application approval date for the study treatment and for the indication being investigated or for 2 years after the development program is discontinued and the FDA notified. After that period, the documents may be destroyed subject to local regulations with prior written permission from the Sponsor. If the Investigator wants to assign the study records to another party or move them to another location, the Sponsor must be notified in advance.

If the Investigator cannot guarantee the archiving requirement at the study site for any or all of the documents, special arrangements must be made between the Investigator and the Sponsor to store these in a sealed container outside of the study site so that they can be returned sealed to the Investigator in case of a regulatory audit. When source documents are required for the continued care of the subject, appropriate copies should be made for storing outside of the study site.

